Missing data: We will document missing data and classify it by variable and study arm. We will then assess if there are relationships between missingness and covariates such as demographics, study arm, or year of study entry. In the analysis of the study hypotheses, all randomized subjects will be included (intention to treat analysis). Missing outcome data will be imputed as failure in all study arms. We anticipate very few subjects will be missing outcome data. In the subgroup analyses, covariate data may also be missing. We will impute these variables using multiple imputation following the methodology of Rubin.⁷¹ We will achieve this using the 3-phase SAS/STAT procedure that first creates “m” multiply imputed complete data sets using the MI procedure, then analyzes the “m” complete datasets using a standard procedure, PROC LOGISTIC, and finally generates valid statistical inferences about the missing values by combining the results using the MIANALYZE procedure properly reflecting the uncertainty due to missing values. In summary, the primary analysis of the study hypotheses will be based on intention to treat analysis using all randomized subjects. Subjects with missing outcome data will be retained in the analysis; failure to complete the 3-dose series will be imputed for those missing these data. We consider this to be the most conservative approach to hypothesis testing. We used this approach in our influenza-vaccine text message reminder study.¹³ Multiple imputation will be used for the missing covariate data in subgroup analyses.

In addition as of 10/21/16: Any parents of an adolescent who was <15 years when first vaccinated who is already enrolled and has not yet received their second dose, will get a text message letting them know that there is an important update, that their child now only needs two doses with the second one being 6 months after the first and that we will text them when that dose is due. We have included that text message under documents.

Parents of adolescents first vaccinated before 15 years of age who have not yet received a second dose will receive an updated series of messages to be consistent

with the now 2 dose recommendation in both phrasing and timing (second dose now due 6 months after the first instead of 2 months and is now the last dose.

Recruitment And Consent

Families of adolescents will be enrolled one of two ways. First, they can be given an information sheet by their provider or the nurse describing the study. This will be attached to an enrollment card on which interested families can write their cell phone number. In providing their number they are agreeing to be in the study. This card will be placed in a box in the clinic. Those who do not want to enroll can indicate that as well. Those who are not given an information sheet or do not have a card in the box, due to provider time, will be called and verbal consent obtained from those who are interested. We will identify in EzVac those who received their first HPV vaccine in approximately the last week for whom we do not have a card. On inclusion, either via return of the enrollment card or over the phone, a confirmation text message will be sent to the participant family and delivery status assessed to ensure that the family has a working cellphone with text message.

References

1. Ten great public health achievements—United States, 1900-1999. MMWR Morb Mortal Wkly Rep. Apr 2 1999;48 (12):241-243.
2. National, state, and local area vaccination coverage among children aged 19-35 months—United States, 2011. MMWR Morb Mortal Wkly Rep. Sep 7 2012;61:689-696.
3. National and state vaccination coverage among adolescents aged 13-17 years—United States, 2011. MMWR Morb Mortal Wkly Rep. Aug 31 2012;61(34):671-677.

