to translating health services research measures,⁵⁹ to translate messages to ensure that we have linguistically and culturally equivalent messages in Spanish and English. We will then pre-test the messages at the study sites with families. The research assistant will approach families after the adolescent has received an HPV vaccination, in coordination with the nursing staff. After obtaining informed consent, the research assistant will text parents in real-time, while meeting with the parent, the proposed messages and ask the parent to say back in their own words what the message means to them. This adaptation of the “teach-back” method, commonly used health literacy tool,⁵⁸ verifies that the message conveys the desired information. S/he will then ask families if there was anything confusing about the message and suggestions for change. This process will be iterative until no new changes are made to the messages. Preliminarily, we will complete this process with 20 families. If we do not reach saturation with 20 families, i.e. changes to the messages are continuing to be made, we will continue to recruit using the same sampling plan.

Study Population

Eligibility Criteria:

- Parent of adolescent age 9-17 years
- Adolescent receives their first HPV vaccine dose at study site within last 2 weeks
- Has a cell phone number that can receive a text message
- Parent speaks English or Spanish

Exclusion Criteria

- Intends to move away from the NYC area in the study

Enrollment: Families of adolescents will be enrolled one of two ways. First, they can be given an information sheet by their provider or the nurse describing the study. This will be attached to an enrollment card on which interested families can write their cell phone number. In providing their number they are agreeing to be in the study. This card will be placed in a box in the clinic. Those who do not want to enroll can indicate that as well. Those who are not given an information sheet or do not have a card in the box, due to provider time, will be called and verbal consent obtained from those who are interested.

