literacy.⁶³ Therefore, all participants in this arm will receive some text messages related to the most common HPV vaccine related health literacy needs. The text messages have been attached to the protocol.

Arm 2: Randomized to receive non-enhanced text message reminders: Will receive non-enhanced text reminders notifying them when the next dose is due. They will receive messages in parallel timing to Arm 1. These will not include vaccine health literacy-promoting information and will be similar to those used in our previous adolescent studies.^{20,14} These are also attached to the protocol. Based on our preliminary studies, all text messages will be personalized and designed to be from the patient's medical home. In our previous studies, parents indicated that they wanted their child's name on the message as well as that it was being sent on behalf of the clinic.^{16,19} The recipient will be the parent based on our previous work. We will text the cell phone number listed in the registration system, indicative of the parent who is to be contacted regarding medical care. Messages will be sent in English or Spanish based on the language preference of the participant. Throughout the study, participants will have the option to stop receiving text messages by replying to a text message with the word "quit" or "stop" in English or the corresponding commands in Spanish. Participants can request help by texting "help". They can also call the study team. These instructions will be given in a text message. After the first message sent to categorize those in Arm 1 and the parallel-timed message for Arm 2, preliminarily, we will send the first series of automated weekly reminders, beginning around d35 after the second HPV vaccine dose due date and will end two weeks after the vaccine is first over-due. Two booster doses will then be sent 28 and 42 days later, if the child has not been vaccinated. We will repeat the intervention beginning approximately d35 after second dose as a reminder for the third dose. The messages will be the same but refer to the third dose. The hospital's immunization registry will be queried before the third dose to ascertain if the patient received the second dose on time. If not, the message schedule for the third HPV vaccine dose will be readjusted for the new due date, based on CDC recommendations for minimal and desired intervals. All the study sites allow walk-ins for second and third doses of HPV vaccine, so no appointment is needed.

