
If the site does not have vaccine, we will send a message to participants due for second or third dose letting them know not to come in yet and that we will inform them when the sites have vaccine available again.

Measures

Outcome Measure: The primary outcome measure is completion of the 3-dose HPV vaccine series within 12 months from date of first dose. A secondary outcome is timeliness of vaccination, defined as time elapsed in days between dose 1 and 2, and dose 1 and 3.

Process Measures: Individual level information from the log files of the text-messaging platform will be collected to demonstrate that the correct messages were sent to each recipient for Arms 1 and 2. We will also determine the percentage of (1) text messages that sent back as undeliverable; and (2) participants opting out of the reminders during the study. We will also determine which specific vaccine health literacy-related information families request via text message, providing, in a prospective fashion, an indication of the most common parent identified HPV vaccine health literacy needs arising at the time that parents are making decisions regarding return for subsequent doses. This prospective information does not currently exist.

Follow-Up: Minimizing attrition and missing outcome data are crucial for valid results. We expect there will be little attrition with respect to outcome data. The hospital immunization registry, EzVac, automatically collects vaccine administrations from the EHR used at the 4 study sites as well as from the New York Citywide Immunization Registry (CIR) as part of the usual patient care, thereby allowing capture of vaccines administered to clinic patients both at study sites and at practices other than study sites in NY City.^{55,56} Thus, we will have outcome data for subjects who receive HPV vaccination at facilities other than a study site. A second important issue is documentation of the intervention. In our previous HPV study, no one dropped out of the study after enrollment;²⁰ in our influenza text message RCT, only 4.5% of the 9,213 families declined further messages.¹³ In addition, we expect only a small number of cell phone numbers will change over the course of the intervention. In our previous adolescent study, the number of cell phone numbers that changed was <2%.¹⁴

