Data Management: Vaccination data will be retrieved from EzVac. All data will be accessed using a password-protected computer in a locked office and stored on a secure server managed by Columbia University IT, and backed up on a daily basis. All data files will be cleaned and edited prior to analysis, under [name] supervision. Data analysis will be performed using SAS (Cary, NC). The programmer will monitor log files of text messages sent, replies received, and "undeliverable" messages and provide summaries to [name] on a daily basis.

Statistical Procedures

Data Analysis: We will first assess the randomization process by comparing baseline variables among the three groups. Hypothesis: Completion and timeliness will be higher in adolescents in families who receive enhanced text message reminders plus usual care vs. non-enhanced text message reminders plus usual care.

Series Completion: HPV vaccine completion rates in EzVac will be compared for all adolescents of participant parents at the end of a 12-month observation period starting at receipt of their first HPV vaccine dose. As in our previous RCT of influenza vaccine reminders,¹³ all primary analyses will be done on an intention-to-treat basis, such that all randomized participants will be included in the analysis whether or not they at some point declined further messages or messages were returned as undeliverable. A secondary analysis will compare completion rates for adolescents of participants who received the entire set of reminders. Study arms will not be combined. Completion rates in the two randomized groups will be compared in the separate combinations delineated above using 2-sided 2 tests at a significance level of $P<0.05$ for each comparison. The number of subjects in each cell is expected to be high enough that the Fisher exact test will not be needed. Asymptotic confidence limits on the differences and relative rate ratios will be calculated.

Sub-group Analyses: We will perform subgroup analyses in different covariate-defined subgroups, for each outcome, to assess the possibility of intervention effects being different in these subgroups. This will be tested by including pre-specified covariates (adolescent: age, gender, year of entry, clinic site, dichotomized visit count; parent: language, previous participation in text message vaccination reminder study),^{42,43,60,61,64-}

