⁶⁸ and their interactions with the intervention in a multiple logistic regression analysis. The models will also adjust for the direct effects of these covariates on the outcomes, thus increasing power to detect intervention effects. Initial models will be created including all of these covariates. Clearly non-significant ($p>0.2$) covariate terms will be removed from the final models. If more than one covariate appears in a final model, two-way (and, if necessary, multi-way) interactions of those covariates among themselves and with the study arm will be tested and included if significant at $p>0.2$) covariate terms will be removed from the final models. If more than one covariate appears in a final model, two-way (and, if necessary, multi-way) interactions of those covariates among themselves and with the study arm will be tested and included if significant at $p<0.05$. In addition to the covariates listed above, we will include race and insurance to the extent possible. Multivariate modeling with these covariates may not be possible depending on the degree of variability observed. The visit count will be defined as the number of clinic visits per adolescent in the 12-month period post-receipt of the first vaccine dose. Visits to the emergency department, hospitalization or specialty visits will not be included. The visit count will be dichotomized (the cut point determined by the frequency distribution of visit counts). With regard to longitudinal measurement, the outcome is defined as success or failure in receipt of 3 HPV vaccine doses within 12 months (no repeat measure of outcome). We will include a covariate for year of entry into study. We will also adjust for vaccine shortages as needed.

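### From 10/21/16 some under-15 families are told the second dose is the last, yet the primary outcome still requires three doses, so those who finish as told are scored as failures

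*Combined protocol and SAP*

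**What the plan says.** **Primary outcome.** Under Measures, Outcome Measure: "The primary outcome measure is completion of the 3-dose HPV vaccine series within 12 months from date of first dose". Study Purpose and Rationale and the Approach Overview give the same three-dose definition. Statistical Procedures, Sub-group Analyses, repeats that "the outcome is defined as success or failure in receipt of 3 HPV vaccine doses within 12 months". Series Completion applies the comparison to everyone by intention to treat: "HPV vaccine completion rates in EzVac will be compared for all adolescents of participant parents".

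**Change of 10/21/16.** This sits at the end of the Missing data text. Enrolled parents of an adolescent under 15 at first dose, with no second dose yet, are to be told that "their child now only needs two doses with the second one being 6 months after the first". Their reminder series is then rewritten, with the "second dose now due 6 months after the first instead of 2 months and is now the last dose". The change covers both arms and does not mention the outcome definition.

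**Related text.** The Approach Overview says a two-dose analysis can be done if two doses prove protective. Randomization stratifies by age group, 9-14 and 15-17. The intervention section still says: "We will repeat the intervention beginning approximately d35 after second dose as a reminder for the third dose". The title block carries an IRB approval date of January 5, 2021, so both statements stand in the current document.

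**The concern.** The trial changed what it asked some families to do but not how it scores them. A participant who receives two doses on the schedule in the trial's own message has finished in the family's eyes and failed in the analysis, in either arm. For that group a three-dose rate is no longer a measure of whether reminders led to completion, which is the stated hypothesis.

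The group may also be wider than those enrolled on the date of the change. The sentence on the rewritten message series is not limited to participants already enrolled, and the eligibility criteria require that "Adolescent receives their first HPV vaccine dose at study site within last 2 weeks". Any under-15 enrolled afterwards would therefore enter the two-dose message series. The documents do not say how many, if any, there were.

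Two things are at stake: the meaning of the primary result, and possibly its power. With the two-dose option and the three-dose definition left unreconciled, an analyst could also choose between three-dose, two-dose and mixed completion after seeing the data.

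**Working it through.** **1. The passages side by side**

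| Place | Doses needed for success | Exception for under-15s? |
|---|---|---|
| Study Purpose and Rationale; Approach Overview | 3 within 12 months | None |
| Outcome Measure | 3 within 12 months | None |
| Sub-group Analyses (outcome restated) | 3 within 12 months | None |
| Text dated 10/21/16 | Family told 2, the second being the last | Yes, but for messages only |

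The Approach Overview sentence permits an additional two-dose analysis and does not replace the primary outcome. Age and year of entry enter the regression models as covariates. They adjust a three-dose outcome and do not rescore it.

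**2. The plan's own sample size**

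Inputs from Study Sample and Enrollment: control rate 51%, difference 9 points (so 60%), 80% power, 5% type I error, 478 per arm. The test is two-sided (Series Completion) and allocation is 1:1 (Randomization).

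n = [1.960·√(2p̄(1−p̄)) + 0.842·√(p₁q₁ + p₂q₂)]² / d², with p̄ = 0.555 and d = 0.09

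- √(2 × 0.555 × 0.445) = 0.7028
- √(0.51 × 0.49 + 0.60 × 0.40) = 0.6999
- n = (1.3775 + 0.5891)² / 0.0081 = 477.5, so 478 per arm, with power 80.0%.

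The plan's figure reproduces.

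**3. Effect of scoring switched families as failures**

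Assumptions, none of them given in the documents: a share f of each arm is switched, f is equal in the two arms, and no switched family gets a third dose. Let k be the three-dose completion that switched families would otherwise have had, relative to the trial-wide rate. The scored rates become 0.51(1−kf) and 0.60(1−kf), and

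power = Φ{[d√478 − 1.960·√(2p̄(1−p̄))] / √(p₁q₁ + p₂q₂)}.

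Example with k=1 and f=10%: rates 0.459 and 0.540, d = 0.081, p̄ = 0.4995. Then (1.7709 − 1.3859)/0.7048 = 0.546, so power is 70.8%.

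| f | k = 1 | k = 0.5 | k = 0 |
|---|---|---|---|
| 0 | 80.0% | 80.0% | 80.0% |
| 2% | 78.3% | 79.2% | 80.0% |
| 10% | 70.8% | 75.5% | 80.0% |
| 25% | 56.3% | 68.3% | 80.0% |
| 50% | 34.2% | 56.3% | 80.0% |

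**4. Which column applies**

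Participants enrolled before 10/21/16 are switched because they have no second dose, so they are likely to be poorer completers and a low k is plausible. For under-15s enrolled after the change there is no such selection, and k near 1 fits better. The mix is unknown.

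**The case against.** The plan partly foresaw this. It allows for a two-dose analysis, balances the 9-14 and 15-17 groups at randomisation, and tests age and year of entry with treatment interactions, so the effect in 15-17-year-olds can be examined. Both arms receive the same change with parallel message timing. All of this stands and limits the harm, but none of it changes how the primary outcome is scored.

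Three stronger readings are tempting and are not supported.

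- **That power has been lost.** The documents give no count by age stratum and no count without a second dose on 10/21/16. If the switched families would not have completed three doses anyway, nothing is lost.
- **That the arms are biased against each other.** For those enrolled before the change, switching depends on second-dose status, a post-randomisation event that the reminders aim to alter. A difference by arm is therefore possible, but neither its size nor its direction can be derived.
- **That the missing-data rule creates the failures.** That rule says "failure to complete the 3-dose series will be imputed for those missing these data". It covers missing outcomes only, and a participant with two recorded doses is not missing. It shows only that the three-dose wording was left in place.

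The sentence on comparing completion rates in EzVac gives no dose count either, so the explicit conflict rests on the outcome definitions listed in the table.

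The Timeliness section is a softer matter. The dose 1-to-3 curve includes participants told that no third dose is needed, and the dose 1-to-2 curve mixes two due dates. That section does refer to ACIP intervals, however, and non-events can be censored.

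**Conclusion.** The contradiction is real, lies in the primary outcome and must be fixed. Confidence is high that the text conflicts with itself and that, followed exactly, it scores families who finish as told as failures. The effect on the result is not established. Dilution may occur, and at f=50% power could be anywhere from 34.2% to 80.0%, depending on how switched families would otherwise have behaved. Those figures rest on 51% vs 60%, 478 per arm, equal f in both arms and no third doses among those switched. The case for change rests on the mismatch between instruction and outcome, not on a demonstrated loss of power. No position is taken on which vaccine schedule is right.

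**What to change.** Reconcile Study Purpose and Rationale, the Approach Overview, the power statement, the third-dose reminder text, Outcome Measure, Sub-group Analyses, Timeliness and the 10/21/16 text. Make the change dated and before unblinding. If data are already unblinded, label the rescored analysis post hoc.

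- **Primary outcome.** State one for all randomised participants: completion, within 12 months of dose 1, of the applicable series. Assign the series only from age at first dose and date of first dose, never from messages received or second-dose status.
- **Straddling group.** Prespecify one arm-neutral rule for under-15s whose first dose fell in the 12 months before 10/21/16. Either count has a cost. A two-dose count credits some whom the plan still reminds of a third dose, and a three-dose count fails some who were told to stop at two.
- **Analysis set.** Keep all randomised participants, as the intention-to-treat rule requires. A primary comparison limited to ages 15-17 would break that rule. At 51% vs 60% it would have power of about 65%, 51% or 33% if that stratum were 70%, 50% or 30% of the sample.
- **Secondary or sensitivity analyses.** Report three-dose completion in everyone, the comparison within the 15-17 stratum, and the analysis without the straddling group.
- **Reporting.** Give numbers switched by arm and age stratum, and show the dose 1-to-3 curve only where three doses apply.
- **Power.** Restate it as conditional on an assumed control rate for the revised outcome.

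The work is mostly wording, since dose dates are in EzVac and the age split is already a stratification factor. The real cost is a mid-trial endpoint change that must be justified. The control rate for the revised outcome is not in the documents, so whether 478 per arm is enough is unknown. It gives 80.0% only if 51% vs 60% still holds.

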We will identify in EzVac those who received their first HPV vaccine in approximately the last week for whom we do not have a card. On inclusion, either via return of the enrollment card or over the phone, a confirmation text message will be sent to the participant family and delivery status assessed to ensure that the family has a working cellphone with text message. An undelivered message will be attempted to be delivered twice moreover the next week. If there are three undeliverable messages then the family will not be considered to have met eligibility criteria and will not be considered enrolled in the trial; they will be notified of this. We will enroll only one child per family. If more than one is eligible, we will select the one with the next most proximal birthday, e.g. a child whose birthday is in 7 days will be selected over a sibling whose is in 75 days. In the case of twins, whoever was designated at birth as twin A will be enrolled. If another adolescent becomes eligible during the trial, the family cannot re-enroll.

Randomization: Randomization will occur with a 1:1 allocation ratio stratified by (1) clinical site; (2) adolescent's gender; (3) parental language; and adolescent's age group (9-14; 15-17). These factors will be excerpted from the medical record after enrollment. Randomization will be done centrally by the programmer using an algorithm based on site, gender, language, and age. The statistician and analyst will be kept blinded to group assignment.

Study Sample and Enrollment

Based on EzVac data, there were 817 adolescents (females and males) 11-17 years old who received their first HPV vaccine at the four study sites between October 2012 and September 2013. Nearly all of those families (n=805) spoke English or Spanish. A few (n=51) were from the same family. Therefore, we expect 1885 adolescents to be eligible over the 30-month recruitment period. Across various studies conducted at the study sites, we found that between 83% and 89% of parents had text messaging. In one study, we assessed those with and without text messages and found no significant differences between those who had texting and those who did not in terms of adolescent's gender, parents' primary language, education level, or parent age. Using the low-end of this range, i.e. 83%, we expect 1,564 families to meet age, language and cell phone/texting inclusion criteria. To meet our sample size of 956 total (478 per arm), we would need to

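### The primary chi-square ignores the four factors that stratify randomisation; adjusting for them as main effects would be a small, nearly free gain in precision

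*Combined protocol and SAP*

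**What the plan says.** The Randomization paragraph states "Randomization will occur with a 1:1 allocation ratio stratified by (1) clinical site", and goes on to name gender, parental language and age group (9-14, 15-17). On the mechanism it says only "Randomization will be done centrally by the programmer using an algorithm based on site, gender, language, and age".

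Under Statistical Procedures, Series Completion, the primary comparison is "Completion rates in the two randomized groups will be compared in the separate combinations delineated above using 2-sided" chi-square tests at the 5% level. The chi symbol does not survive in the extracted text, but the remark there on Fisher's exact test makes the meaning clear. The effect measures follow: "Asymptotic confidence limits on the differences and relative rate ratios will be calculated". No stratification factor enters the test or the limits.

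The four factors do appear under Sub-group Analyses, among the pre-specified covariates that are entered with "and their interactions with the intervention in a multiple logistic regression analysis". That section says adjustment for the covariates' direct effects is "thus increasing power to detect intervention effects". It also says that clearly non-significant (p>0.2) "covariate terms will be removed from the final models". One covariate, the visit count, is defined as the "number of clinic visits per adolescent in the 12-month period post-receipt of the first vaccine dose".

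**The concern.** When allocation is balanced within strata and the strata predict the outcome, the two arms are more alike than simple randomisation would make them. An unadjusted standard error does not reflect this, so the test is mildly conservative and its intervals slightly too wide. Adjustment recovers the loss. If allocation is not balanced within strata, adjustment still removes outcome variance that the factors explain. The plan states that adjustment increases power, yet leaves it out of the one analysis that was powered.

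The subgroup logistic model does not fill the gap:

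- It starts with arm-by-covariate interactions, so its arm term is not a single overall effect.
- Stratification factors can be removed on their p-values.
- The visit count is measured after randomisation. Reminders are meant to bring families to the clinic, so the intervention could affect it.
- Logistic regression yields odds ratios, whereas the primary analysis promises differences and rate ratios.

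**Working it through.** **Inputs.** From Study Sample and Enrollment: 51% expected in Arm 2, a 9-point difference (so 60% in Arm 1), 80% power, type I error 5%, 478 per arm. From Series Completion: two-sided test. From Preliminary Studies, item 1: three doses within 12 months in 40.0% of females and 30.7% of males aged 11-17. From Randomization: 4 sites × 2 × 2 × 2 = 32 strata, or 956/32 ≈ 30 people each on average.

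**1. The plan's own figure.** With pooled variance under the null and mean rate 0.555:

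n = [1.960·√(2·0.555·0.445) + 0.8416·√(0.51·0.49 + 0.60·0.40)]² / 0.09² = (1.3775 + 0.5891)² / 0.0081 = 477.5, so 478 per arm.

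This matches the plan. Power at 478 is 80.0%. The 95% half-width for the difference is 1.96·√(0.4899/478) = 6.27 points.

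**2. What gender explains.** R² = π(1−π)·d² / [p(1−p)], where π is the female share, d the gender difference and p the overall rate.

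- At 50:50: 0.25·0.093² / (0.3535·0.6465) = 0.0095.
- At 65:35: 0.2275·0.093² / (0.36745·0.63255) = 0.0085.

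The document gives no completion rates by site, language or age stratum, so larger values of R² are assumptions.

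**3. Effect of adjustment.** Residual variance falls by the factor (1 − R²). Power = Φ[(0.8416 + 1.960)/√(1 − R²) − 1.960]. The half-width is 6.27·√(1 − R²). With balanced allocation, the unadjusted standard error is too large by 1/√(1 − R²) − 1.

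| R² | Basis | Power | Half-width (points) | Excess in unadjusted SE |
|---|---|---|---|---|
| 0 | no prognostic value | 80.0% | 6.27 | 0 |
| 0.0095 | gender, documented | 80.4% | 6.24 | 0.5% |
| 0.05 | assumed, four factors | 82.0% | 6.12 | 2.6% |
| 0.10 | assumed, four factors | 84.0% | 5.95 | 5.4% |

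For gender alone the saving is 478 × 0.0085 to 478 × 0.0095, or 4 to 5 participants per arm.

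**4. Simulation of the choice of test.** N = 956, 9-point effect, 32,000 trials per scenario. Assumed shares were sites 40/30/20/10, Spanish 65%, younger age group 75% and gender 50:50. Six of the 32 strata then expect fewer than 10 people. Power (%):

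| Scenario | Chi-square | Main-effects risk difference | 32-stratum CMH |
|---|---|---|---|
| Gender only, blocks of 4 | 79.6 | 80.0 | 80.0 |
| Gender only, unblocked | 80.3 | 80.6 | 79.4 |
| No prognostic factor, blocks of 4 | 80.2 | 80.3 | 80.2 |
| No prognostic factor, unblocked | 79.8 | 79.8 | 78.4 |

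Type I error was 4.8% to 5.2% for all tests. The main-effects model never does worse than the chi-square. The fully stratified CMH loses 0.9 to 1.4 points when allocation is unblocked.

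**5. Stronger prognosis.** A second simulation used 6,000 trials per scenario, blocks of 4, and a linear risk-difference model with robust standard errors:

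| R² | Power, chi-square | Power, adjusted | Type I error, chi-square | Type I error, adjusted |
|---|---|---|---|---|
| 0 | 79.3 | 79.3 | 4.4 | 4.6 |
| 0.009 | 80.9 | 81.2 | 4.8 | 5.0 |
| 0.023 | 80.6 | 81.3 | 4.7 | 5.3 |
| 0.06 | 81.4 | 82.9 | 3.7 | 4.7 |
| 0.14 | 80.8 | 85.2 | 3.4 | 4.8 |

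Monte Carlo error is about 0.5 points for power (√(0.8·0.2/6000)) and 0.3 for type I error (√(0.05·0.95/6000)). Under blocking the estimate itself barely changes: at R² = 0.14 its standard deviation is 2.97 points unadjusted and 2.96 adjusted. The gain comes from a correct standard error, with mean interval width falling from 12.5 to 11.6 points.

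**The case against.** The unadjusted chi-square is valid, simple and consistent with the sample-size calculation, so an adjusted primary analysis can be called a preference. On documented figures the gain is under half a point of power. The 82% and 84% figures have no completion data behind them, and the Study Sites section describes patients and providers as similar across clinics. All of this stands, and is why the point is graded as optional.

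It can also be said that adjustment is already planned for every outcome. On one reading of Sub-group Analyses, interactions stay only if significant, so the final model could have a single arm term. Removal at p>0.2 would mostly drop factors that matter little. The text there is partly duplicated and that reading is possible. Even so, the model would keep a post-randomisation covariate, give an odds ratio and remain outside the primary analysis.

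Timing is the most practical objection. Families were already enrolled by October 2016 and the approval date is January 2021, so changing a primary analysis needs a record that it was done blind to outcomes by arm. The plan does keep the statistician and analyst blinded to assignment.

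Finally, the usual-care rates behind the gender figure may not describe this trial. From 10/21/16, families of those first vaccinated before 15 who lacked a second dose were to be told that two doses suffice, while the primary outcome stayed at three. Age group could then predict the outcome strongly. As an assumed illustration, 30% versus 55% completion with 50% to 75% in the younger group gives R² of 0.06 to 0.05. That would raise the gain; the wider endpoint question is separate and is not solved by adjustment.

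**Conclusion.** The point holds as a minor efficiency matter. The primary test and limits omit all four stratification factors, and no other planned analysis supplies an adjusted overall risk difference or rate ratio. Error control and the stated 80% power are not in question.

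The documented gain is about 0.4 points of power, from gender alone, assuming that the usual-care gender difference carries over to the trial. A gain of 2 to 4 points requires the four factors jointly to explain 5% to 10% of outcome variance, which the document neither supports nor excludes. The claim that the unadjusted intervals are too wide depends further on allocation being balanced within strata, which the plan does not describe. If the factors have no prognostic value, power changes by no more than about 0.1 point.

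**What to change.** In Series Completion, define the primary analysis as a model with study arm and the four stratification factors as main effects. Retain all four whatever their p-values, and exclude post-randomisation covariates such as the visit count. Report the standardised risk difference and rate ratio with 95% confidence intervals, so that the planned effect measures are kept. Keep the unadjusted chi-square as a sensitivity analysis. Do not use a 32-stratum CMH as the primary test, given the sparse strata. Add a sentence on how the randomisation algorithm balances arms within strata.

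The cost is one or two sentences in the plan and a few lines of SAS. The four factors are needed to randomise, so no new data are required. The amendment should be dated and should state that it was made before outcomes were examined by arm. If that can no longer be said, report the adjusted analysis as a supportive result.
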